### **Missing Data**

Although every effort will be made to minimize the amount of missing data, some level of missing data will be unavoidable for a variety of reasons. In general, data may be missing due to subject's early withdrawal from study. Patients discontinuing early from the study and reasons for withdrawal will be summarized by treatment group to see if any biases in the analyses may have been created by any differences between groups. For the study of time-to-event endpoints, patients completing the study and not experiencing an event of interest are considered censored to the event. The impact of missingness will be minimized in the analysis of the primary endpoint by performing the analysis using Kaplan-Meier estimate, where participants will be censored at their last assessed time point. The procedures outlined below describing what will be done when data are missing may be refined during the blind review of the data.

For this Phase II study, missing data imputation will only be done for the primary and secondary biochemical outcomes (i.e., plasma levels of citrulline, arginine, ornithine, and NOx). For the analysis of other safety and secondary endpoints, no imputation will be done for missing values.

Missing biochemical data, it will be minimized operationally as we are setting up significant oversight on sample logistics. Nonetheless, given the longitudinal nature of data collection for biochemical measures, there exist the possibility of data truncation due to patient death.

The analyses for the biochemical measures will be fitted with a mixed effects model (with random intercept and slope). The advantage of using a mixed effects model is the use of all available cases and only excluding patients with missing biochemical values at all data collection periods. The model will analyze patients who have values missing only at some assessment periods by allowing for the missing data using the within and between patient correlations. However, the mixed effects modeling approach may not necessarily reduce all the bias when the missing mechanism is informative or not-missing-at-random (NMAR). As a sensitivity analysis, we will apply an imputation approach based on pattern mixture modelling. Initially, we will assume an ignorable missingness mechanism and use multiple imputation to impute missing values. The pattern mixture modelling will be used to adjust the imputed values by a fixed value. Next, the mixed effects model will be fitted using the adjusted values for each imputed dataset and Rubin's rule will be used to combine the results.

While we have outlined potential strategies to handle missing data, the primary goal will be to mitigate the level of missingness utilizing the following steps: (1) the protocols and informed consent forms will clearly differentiate treatment discontinuation from study withdrawal; (2) site investigators will be trained about the importance of retention and steps to prevent missing data; (3) the consent forms will include a statement educating patients about the continued scientific importance of their data even if they discontinue study treatment early; (4) we will continue following patients after discharge via telehealth visits or other modalities (e.g., phone, texts, and emails); (5) we will take steps to be able to ascertain vital status in all randomized patients.

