or NO production (3) Labeled citrulline leaves the plasma and is metabolized by a full turn of the urea cycle before reentering as arginine, (4) Oral administration of ^{15}N -arginine results in a nearly five-fold greater recovery of tracer in $^{15}\text{NO}_3$ than when an equimolar amount of tracer is given intravenously, documenting significant splanchnic production of NO. Administration of IV citrulline significantly bypasses the splanchnic circulation, thus limiting the splanchnic production of NO. (5) About 15% of the plasma arginine turnover is associated with urea formation; only 1.2% is associated with NO production. As arginase is upregulated in sepsis, the amount of arginine available as substrate for NOS is further reduced. Although this may decrease NO production somewhat (likely limited due to the low percentage of arginine converted to NO normally), it also alters homeostasis by uncoupling NOS and limiting the amount of NO available to scavenge free radicals. Citrulline is resistant to arginase and our data demonstrate that citrulline administration produces a more consistent plasma level of arginine than arginine administration itself.

3.4 COVID-19 (SARS-CoV2) and Acute Hypoxemic Respiratory Failure Requiring Invasive Mechanical Ventilation

Although reports in the US literature on COVID-19 (SARS-CoV2) and critical illness is limited, a recent case series published in the New England Journal of Medicine detailed the clinical course of 24 critically ill adults with acute hypoxemic respiratory failure and confirmed COVID-19 infection (SARS-CoV2) in Seattle, Washington at 3 hospitals in the University of Washington health care system (106). The mean age was 64 +/- 18 years with a range of 23-97 years and 63% were male. Patients had symptoms an average of 7 days before hospital admission. Of the 24 patients, 18 or 75% required invasive mechanical ventilation but after exclusion of 3 patients who had "do not intubate" directives the percentage was to 18/21 or 86% requiring invasive mechanical ventilation. The median duration of invasive mechanical ventilation was 10 days (IQR 7-12) and overall mortality was 50% in this critically ill population.

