6.2 Inclusion Criteria

Participant eligibility is determined based on the selection of criteria detailed below:

1. Age 18-65 years.
2. Clinical evidence of COVID-19 (SARS-CoV2) infection, defined as a positive COVID-19 laboratory test plus evidence of an acute hypoxic respiratory illness requiring oxygen.
3. Admitted and transferred to floor without intubation.

6.3 Exclusion Criteria:

Patients meeting any of the following criteria will not be eligible for participation in the study:

1. No consent/inability to obtain consent
2. Patient, surrogate, or physician not committed to full support
3. Malignant or other irreversible condition and estimated 28-day mortality $\geq 50\%$
4. Moribund patient not expected to survive 48 hours (as defined by primary medical team) from start of study infusion
5. End-stage Liver Disease as defined by Child-Pugh Score > 9
6. Currently enrolled in, or participated in another study of an investigational compound within the last 30 days
7. Pregnant female, or female who is breast feeding
8. Allergy to L-citrulline or arginine or any citrulline- or arginine-containing product
9. Patient not otherwise suitable for the study in the opinion of any of the investigators
10. Requirement for intubation and invasive mechanical ventilation before study enrollment

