## Primary Endpoints

### Primary Clinical Endpoint

- The primary clinical efficacy variable is time to intubation event in hours from the start of study infusion.

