### Statistical Method for the Primary Clinical Efficacy Endpoint

Kaplan-Meier estimates of the survival functions will be graphically displayed for each treatment group. Kaplan-Meier quartiles (25th percentile and median) with two-sided 95% confidence intervals will be calculated if applicable. In addition, time to intubation will be summarized via displaying number of

subjects at risk, the percent of subjects that are censored, and Kaplan-Meier event rates with two-sided 95% confidence intervals.

A log-rank test stratified by the randomization stratification factor (age group) will be used to compare the time to intubation of the two treatment groups. The hazard ratio of IV Citrulline compared with placebo and its corresponding two-sided 95% confidence interval will be estimated using a Cox proportional hazards (PH) model with treatment groups as the independent variable and stratified by the age group.

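### The primary endpoint has no rule for death before intubation: read literally, an unintubated death is censored, and it could then read as delayed intubation

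*SAP*

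**What the plan says.** SAP, Primary Clinical Endpoint: "The primary clinical efficacy variable is time to intubation event in hours from the start of study infusion". Under the statistical method for that endpoint, "A log-rank test stratified by the randomization stratification factor (age group) will be used to compare the time to intubation"; a Cox model stratified by age group gives the hazard ratio, and Kaplan-Meier curves, quartiles and event rates are reported. Death is part of none of these.

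SAP, Missing Data, holds the only censoring rules. For time-to-event endpoints in general, "patients completing the study and not experiencing an event of interest are considered censored to the event". For the primary endpoint, "participants will be censored at their last assessed time point". The second rule is the one that reaches a patient who dies, because such a patient has arguably not completed the study.

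The same section recognises truncation by death, but for the biochemical measures only, and it limits imputation likewise: "missing data imputation will only be done for the primary and secondary biochemical outcomes". Hospital mortality is a separate secondary endpoint, with Fisher's exact test, a log-rank test and a Cox hazard ratio.

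**The concern.** Death before intubation is a competing event: once it happens, intubation cannot. The planned analysis removes that patient from the risk set with the same status, not intubated, as a patient who came off oxygen and went home. Severe disease is expected (both sample size sections take mortality as 50% among patients who progress to ICU care), so such deaths are foreseeable.

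Two things are at stake. If one arm has more deaths among patients who were about to be intubated, that arm shows fewer intubations and a hazard ratio that favours it. Separately, 1 minus Kaplan-Meier with deaths censored estimates the intubation risk in a setting where nobody dies. It does not estimate the proportion of patients actually intubated.

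**Working it through.** **The plan's own figure.** Both sample size sections state 81% power for 60 patients, hazard ratio 0.46 (3/6.5 = 0.46), two-sided 0.05. Freedman's formula is power = Φ(√d × (1 − HR)/(1 + HR) − 1.96). With d = 60 events: √60 × 0.54/1.46 − 1.96 = 0.905, and Φ(0.905) = 81.7%. So 81% is reproduced if essentially all 60 patients are intubated (59 events give 81.1%). Schoenfeld's formula gives 85.3% at 60 events and needs 54 events for 81%. The SAP does not name its formula. On either, the calculation leaves little room for patients who die unintubated.

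**Assumptions, because the documents give no figures.** Intubation times are exponential with a placebo median of 3 days, so λ = ln 2/3 = 0.231 per day. The drug has no true effect on deterioration. Unintubated deaths occur in the citrulline arm only, with share s set at 10%, 20%, 33% or 50%.

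*Case 1: deaths replace intubations.* A share s of the citrulline patients who reach the point of intubation die instead. The intubation hazard in that arm is (1 − s)λ, so with deaths censored HR = (1 − s)λ/λ = 1 − s. With death counted as an event, both arms have hazard λ and HR = 1.

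*Case 2: deaths independent of intubation risk.* The intubation hazard is λ in both arms, so HR = 1. The added death hazard is λs/(1 − s), so the intubation-or-death HR is 1/(1 − s).

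Simulation: 20,000 trials per row, 30 per arm, follow-up to day 10, unstratified log-rank and Cox. The percentage is the chance of a significant result favouring citrulline (nominal 2.5%).

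| s | Case 1, deaths censored: HR | % | Case 1, intubation or death: HR | Case 2, deaths censored: HR | % | Case 2, intubation or death: HR |
|---|---|---|---|---|---|---|
| 10% | 0.900 | 5.8 | 1.000 | 1.002 | 2.6 | 1.114 |
| 20% | 0.800 | 11.5 | 1.000 | 1.000 | 2.7 | 1.255 |
| 33% | 0.669 | 25.9 | 1.000 | 1.005 | 2.6 | 1.500 |
| 50% | 0.499 | 56.2 | 1.000 | 1.004 | 2.3 | 2.017 |

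Follow-up to day 60 gave similar results. In case 1, 10% and 20% mean about 2.7 and 5.4 unintubated deaths against none by day 10 (54.1 − 51.4 and 54.1 − 48.7 mean events). The design HR of 0.46 would be reached with no benefit at s = 1 − 0.46 = 54%.

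A second simulation of case 1 assumed that only 60% of patients deteriorate, with 28 days of follow-up and 4,000 trials per row. Shares of 0, 10%, 20% and 30% gave mean HR 1.01, 0.90, 0.80 and 0.70, and significance favouring citrulline in 2.1%, 4.7%, 9.1% and 16.2% of trials. The HR is the same function of the share; the false-positive rate is lower because there are fewer events.

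**Event rates at day 10, s = 20%, citrulline arm** (λ × 10 = 2.3105).
- Case 1: 1 − Kaplan-Meier = 1 − exp(−0.8 × 2.3105) = 84.3%; actually intubated = 0.8 × (1 − exp(−2.3105)) = 72.1%.
- Case 2: 1 − Kaplan-Meier = 1 − exp(−2.3105) = 90.1%; actually intubated = 0.8 × (1 − exp(−2.3105/0.8)) = 75.5%.

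The Kaplan-Meier event rate is too high in both.

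**The case against.** Neither document says that death is censored; this is inferred from a general rule. That is right, and the supportable defect is an unstated rule whose literal reading is censoring.

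The log-rank test and Cox model remain a valid comparison of cause-specific intubation hazards. This also stands. A reader might infer that any imbalance in unintubated deaths biases the hazard ratio; case 2 shows that it does not. Nor does replacement in equal shares: (1 − s)/(1 − s) = 1. In a double-blind trial there is no stated reason why new limits on care should differ by arm. Hypotension, the theoretical risk named in Protocol 11.5, need not kill patients who were about to be intubated, so such deaths may be closer to case 2.

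A reader might also take support from the case series in Protocol 3.4: "Of the 24 patients, 18 or 75% required invasive mechanical ventilation", three others had do-not-intubate directives, and half of the series died. It does not support an arm imbalance. It is one group of critically ill patients aged 23 to 97, it does not say that those three died, and Protocol 6.3 excludes at entry any case of "Patient, surrogate, or physician not committed to full support".

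Nor are death and recovery treated identically in every respect. They share a censoring status, but Protocol 11.5 continues data collection after weaning, so the censoring times can differ.

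Other safeguards exist: the mortality analyses, the comparisons of intubation proportions, the safety look after 20 patients, the summary of withdrawals by arm, and the option to refine missing-data procedures at blind review. They would make an imbalance visible, but none sets a rule for death in the primary analysis. Protocol 10.2 promises sensitivity analysis for missing data and uncertainty; the SAP supplies it only for the biochemical data. The mortality comparison is sized for 50% against 17% (78.8% power on recalculation, against the stated 80%) and is subject to the Hochberg adjustment, so a moderate imbalance could pass without significance. The entry exclusion does not cover sudden death or a later change in goals of care.

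**Conclusion.** The gap is certain: intubation is the only event, the general censoring rule has no exception for death, and no competing-risk or combined analysis is planned for the primary endpoint.

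The bias is conditional. It needs deaths that differ by arm and that replace intubations; the HR is then about 1 minus the share replaced in one arm. The 10% to 50% range, the exponential times and the one-arm deaths are assumptions, and the documents give no figure for the share. If deaths are independent of intubation risk, there is no false delay, but the primary result does not show the harm. The overstatement of intubation incidence by the Kaplan-Meier event rates applies in both cases.

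A reader might conclude that excess deaths would appear as benefit, or that delay should be claimed only if a combined estimate agrees. The documents support neither: the first depends on an unknown mechanism, and the second is a preference about decision rules for a Phase II trial.

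**What to change.** Before unblinding, amend the SAP's Missing Data section and the statistical method for the primary endpoint:

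1. State expressly how a death before intubation is handled in the primary log-rank test and Cox model, including the time assigned to it.
2. Add a pre-specified key sensitivity analysis of time to intubation or death without intubation, using the same age-stratified log-rank test and Cox model in the ITT population.
3. Report the planned event rates as cumulative incidence of intubation, with death as a competing event.
4. Tabulate intubations and unintubated deaths by arm.

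The cost is SAP wording, one extra model and one table. Deaths and their times are already needed for the time-to-death analysis, and the SAP already commits to steps to ascertain vital status in all randomised patients. The small downside is that the combined endpoint mixes two outcomes, so both components must be shown beside it.

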2.0 STUDY SUMMARY

Title: Prospective, Randomized, Double-Blind, Placebo-Controlled Phase II Trial of Intravenous L-Citrulline to Delay and Potentially Prevent the Need for Invasive Mechanical Ventilation for Acute Hypoxemic Respiratory Failure in Patients with COVID-19 (SARS-CoV2) Illness.

Objective: To evaluate safety and efficacy of a bolus loading dose and continuous intravenous infusion of L-Citrulline compared to placebo in patients hospitalized with COVID-19 infection (SARS-CoV-2).

Hypothesis: Intravenous L-citrulline administration will safely restore the homeostasis of nitric oxide synthase by increasing both plasma citrulline and arginine levels. We also reason that restoration of citrulline/arginine balance through citrulline administration will safely re-establish homeostasis of NOS, lower oxidative stress, and reduce inflammation, thereby delaying and potentially preventing the need for invasive mechanical ventilation in patients hospitalized with COVID-19 infection (SARS-CoV-2).

Study Design:	
Prospective, randomized, placebo-controlled, double-blind design.
 
 1. Enrollment: approximately 6-9 months 2. Plasma citrulline and arginine levels at day 4 will represent the primary biochemical variable. 3. Vasomotor stability, as measured using a vasopressor dependency index (VDI), through study day 10, will represent the primary safety variable. 4. The length of time from the initiation of the treatment to an intubation event for invasive mechanical ventilation measured in hours will represent the primary clinical outcome. 5. Patients will be followed until hospital discharge for mortality, ICU and hospital lengths of stay, and a requirement for invasive mechanical ventilation and non-invasive mechanical ventilation with high flow nasal cannula or BiPAP as additional clinical endpoints. A further comparison will be performed at D28 and D60 based on telephone follow up for those discharged earlier. 6. Patients will exit the study early (prior to 10 days) if they recover and no longer require oxygen therapy.

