5.2 Treatment Arms and Study Drug Administration

All study material infusions (including the initial boluses) will be administered intravenously through a dedicated peripheral line or a dedicated port of a central line using a volumetric or syringe pump. The infusion will be restarted as soon as possible after any stoppages and will continue through day 10 unless the patient exits the study early. Regardless of amount of time the infusion is stopped, time missed during any stoppage will not be added to the end of the infusion.

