11.5 Potential Risks

All patients will reside in a hospital unit or intensive care unit environment, where close monitoring can be achieved and rapid response to any potential adverse event, including hypotension, will occur. Should a patient improve and be weaned off all oxygen support prior to completion of the study drug infusion, the study drug will be stopped but data will continue to be collected. Patients will be monitored by the bedside or ICU nurse for the duration of the infusion per standard unit protocol. The investigator and/or coordinator will be available by pager 24 hours a day 7 days a week to answer any questions that the bedside nurse has.

All patients will have blood drawn for research purposes. The risks of drawing blood are uncommon and may include bleeding and bruising. Commonly, having blood drawn is painful, and rarely can lead to infection at the site of the blood draw. It is anticipated that most of the blood obtained for research purposes will be obtained through existing intravenous peripheral, central, or arterial catheters since these patients routinely have such catheters while in the intensive care units. The amount of blood drawn is minimal and represents a small percentage of the amount of blood taken during a standard hospital or ICU stay and will not represent a significant risk to the patient.

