## **STUDY ASSESSMENTS**

The assessment of efficacy will include collection of plasma for analysis of citrulline and arginine levels at 2 hours, 12 hours, and the alternating morning of study days the infusion is running for a maximum of

10 days, i.e., on days 2, 4, 6, 8 and 10. A patient will exit the study early if they have been weaned off all oxygen support before 10 days. Additional efficacy measures will include clinical outcomes, including progression of acute lung injury and lengths of hospital and ICU stay.

The assessment of safety will include collection of hemodynamic measurements at least every 4 hours on a hospital unit and--if a patient is critically ill in an ICU--hourly while the study material is infusing and for 12 hours after completion of the infusion in each patient. Hemodynamic measurements will be converted to a vasopressor dependency index for analysis if a patient becomes critically ill. Adverse event reporting will also serve as a means of safety analysis. Additional safety measures will be biochemical and hematologic laboratory measurements. The biochemical laboratory measurements, including liver function tests (ALT, AST, bilirubin, alkaline phosphatase), kidney function tests, D-dimer tests, CRP and electrolytes, along with hematologic laboratory measurements, including complete blood count and platelet count, will be collected when available for any study day in order to evaluate for adverse events.

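### The SAP does not define the censoring date for patients who come off oxygen unintubated; if it is study exit, the Kaplan-Meier rates overstate the proportion intubated

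*SAP*

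**What the plan says.** The SAP's Missing Data section relies on a Kaplan-Meier analysis of the primary endpoint "where participants will be censored at their last assessed time point". It also treats patients who complete the study without the event as censored. Neither rule gives a date or a horizon, and neither mentions recovery.

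For a patient who comes off oxygen without intubation, the documents point in different directions:

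- **Leaves the study.** SAP, Study Assessments (the same sentence is in Protocol 5.1.2): "A patient will exit the study early if they have been weaned off all oxygen support before 10 days". Protocol 2.0, Study Design item 6: "Patients will exit the study early (prior to 10 days) if they recover and no longer require oxygen therapy". Protocol 5.2 ties the infusion to the same idea: it "will continue through day 10 unless the patient exits the study early".
- **Stays in follow-up.** Protocol 11.5, on exactly this patient: "the study drug will be stopped but data will continue to be collected". Protocol 2.0, Study Design item 5: "Patients will be followed until hospital discharge for mortality, ICU and hospital lengths of stay, and a requirement for invasive mechanical ventilation", and "A further comparison will be performed at D28 and D60 based on telephone follow up for those discharged earlier".
- **Ventilation data.** Protocol 7.2.2 collects invasive ventilator settings from Day 12 to discharge. Appendix A marks invasive ventilation status only to Day 11. At Days 28 and 60 it marks hospital and ICU status but not ventilation.

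The SAP's method for the primary endpoint reports Kaplan-Meier event rates, the 25th percentile and the median (the quartiles if applicable), a log-rank test stratified by age group, and a Cox hazard ratio. It names no competing-risk method.

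**The concern.** The last assessment of a recovered patient could be the end of oxygen, Day 11, discharge, Day 28 or Day 60. The choice changes what the reported rates mean. Coming off oxygen is recovery, so it is informative about later intubation. A Kaplan-Meier curve that censors there assumes that the patient would have gone on to face the intubation risk of those still on oxygen. One minus the curve then no longer estimates the proportion of the arm intubated, and it will disagree with the crude proportions that the SAP compares as secondary endpoints.

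Death without intubation raises the same issue on any reading, because the SAP gives no rule for it. The choice also affects what the primary test can detect. The protocol's hypothesis is "thereby delaying and potentially preventing the need for invasive mechanical ventilation", and censoring at exit cannot show prevention that works through faster recovery alone.

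**Working it through.** **1. The plan's own figure.** Protocol 10.4 and the SAP's Sample Size section state 81% power for 60 patients and a hazard ratio of 0.46. Freedman's formula with 60 events gives Φ(√60 × (1 − 0.46)/(1 + 0.46) − 1.96) = Φ(0.905) = 0.817, so the figure reproduces. It counts nearly every patient as an event (Schoenfeld's formula needs 54), so no recovery rate can be drawn from it.

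**2. Kaplan-Meier rate with censoring at exit.** Assumptions, none of them from the plan except the 86% (18 of 21 critically ill patients, Protocol 3.4): constant hazards; a proportion p truly intubated and 1 − p recovered; median m days to whichever comes first. Then h = p ln2/m for intubation and r = (1 − p) ln2/m for recovery.

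- Kaplan-Meier rate = 1 − exp(−h t)
- True proportion = p(1 − exp(−(h + r) t))

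Example, p = 0.30, m = 3, t = 10: h = 0.0693, so the Kaplan-Meier rate is 1 − exp(−0.693) = 50.0%. The true proportion is 0.30 × (1 − exp(−2.310)) = 27.0%. The excess is 23.0 points.

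| p | Day 10 excess, m = 3 | Day 10 excess, m = 5 |
|---|---|---|
| 30% | 23.0 | 11.5 |
| 50% | 23.5 | 12.5 |
| 75% | 14.8 | 8.4 |
| 86% | 8.8 | 5.1 |

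Simulated arms of 33 (8,000 runs) agree within 0.2 points. About 3.3 (m = 3) or 8.3 (m = 5) of 33 are still at risk at Day 10.

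The range is not a bound. If the plan's 3 days is read instead as the median for intubation alone, the Day 10 Kaplan-Meier rate on placebo is 1 − exp(−10 ln2/3) = 90%. With an assumed median of 20 down to 3 days to come off oxygen, the true proportion is 81% down to 50%, an excess of 9 to 41 points.

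**3. 25th percentile.** Kaplan-Meier: −ln(0.75)/h. True: −ln(1 − 0.25/p)/(h + r). At m = 3:

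- p = 30%: 4.2 against 7.8 days (6.9 against 12.9 at m = 5)
- p = 50%: 2.5 against 3.0 days
- p = 75%: 1.7 against 1.8 days

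The difference is material only when few patients are intubated.

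**4. Recovered patients kept at risk, deaths censored.** Let λ = ln2/m, S = exp(−λt), and d the proportion dying unintubated (assumed 5-10%). Recovered patients still at risk are R = (1 − p − d)(1 − S), and the hazard that Kaplan-Meier sees is pλS/(S + R). The excess over p(1 − S) is 0.5-5.9 points at Day 10 and 0.8-8.4 points at Day 28.

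**5. The test.** Simulated unstratified log-rank, 30 per arm, 28 days, no deaths, 10,000 runs, m = 3. Under no effect, rejection is 5.1-5.7% with censoring at exit and 4.6-5.3% with Day 28. Power, exit against Day 28:

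| Placebo intubated | Hazard ratio 0.46 on intubation only | Same, plus recovery hazard doubled |
|---|---|---|
| 30% | 28% / 23% | 17% / 54% |
| 50% | 46% / 35% | 34% / 73% |
| 75% | 67% / 45% | 59% / 79% |
| 86% | 74% / 53% | not run |

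If the drug only doubles the recovery hazard, results favouring it occur in 2-3% of trials with exit censoring and 16-21% with Day 28 (30-75% of placebo intubated).

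**The case against.** The strongest reply is that the exit reading is the weaker one. Protocol 11.5 addresses this very patient and keeps collecting data. Protocol 2.0 and 7.2.2 follow ventilation to discharge. Protocol 6.1 keeps early stoppers in the intention-to-treat analysis. The SAP itself plans contact after discharge and lets its missing-data procedures be refined at blinded review. This stands as far as it goes: the recovery bias is conditional. It does not remove the conflict, because the SAP's own Study Assessments section says that the patient exits.

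The sizes also rest on assumed rates. The 86% comes from critically ill patients, whereas this trial enrols patients on the floor. Unintubated deaths should be limited by the exclusion of patients not committed to full support.

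Three stronger readings are tempting and are not supported:

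- **The primary test is invalid.** With exit censoring, the log-rank test and Cox model still compare cause-specific hazards, and the simulated error rate is close to 5%. The bias lies in the descriptive rates of each arm.
- **Day 28 censoring must be primary.** This is a choice of estimand. It costs power if the drug lowers only the intubation hazard, and differences in the proportion intubated are already tested as secondary endpoints.
- **The tables would hide recovery.** The five reasons in Patient Disposition do omit it, but they concern study drug. The SAP also summarises reasons for leaving the study by arm and reports the percentage censored.

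**Conclusion.** The gap is certain: the censoring date for the primary endpoint is undefined for patients who recover, are discharged or die unintubated, and the passages on follow-up after oxygen conflict. The consequence is conditional. Read literally, the SAP censors at exit, and its Kaplan-Meier event rates then overstate the proportion intubated by about 5-24 points at Day 10, given constant hazards, 30-86% intubated and a median of 3-5 days. The direction is secure because exit means recovery; the size is illustrative. If follow-up continues, only unintubated deaths inflate the rates, by less at the same settings. The planned test and hazard ratio stand. The point should be fixed, but it does not undermine the primary comparison.

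**What to change.** 1. **Reconcile follow-up.** Bring Protocol 2.0 item 6, Protocol 5.1.2 and the SAP's Study Assessments into line with Protocol 11.5 and 5.2, and Protocol 7.2.2 into line with Appendix A, so that outcome follow-up for intubation continues after oxygen ends. Record intubation status and date at the existing Day 28 contact. This concerns data collection only, not when treatment stops.
2. **State the censoring dates** in the SAP's Missing Data section before unblinding, separately for patients who recover, are discharged, or die unintubated. Report the other reading as a sensitivity analysis. Which one is primary is the sponsor's choice of estimand. In the scenarios above, Day 28 loses about 4-22 points of power at a median of 3 days (3-16 at 5 days) if the drug lowers only the intubation hazard, and gains 20-38 points (median 3 days) if it also speeds recovery.
3. **Report the cumulative incidence of intubation** (Aalen-Johansen) in place of the Kaplan-Meier event rates and quartiles. Treat death without intubation as a competing event and keep recovered patients event-free. If follow-up does end at exit, treat recovery as a competing event too.

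The age-stratified log-rank test and Cox model stay as planned. The cost is one question at an existing call, some protocol and SAP wording, a little more analysis, and rates less comparable with trials that report Kaplan-Meier.
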